4.1.4 Method of assigning patients to treatment groups

Eligible patients will be randomised to receive either xentuzumab in combination with everolimus and exemestane or placebo in combination with everolimus and exemestane in a 1:1 ratio according to a randomisation plan. The assignment will occur in a blinded fashion via Interactive Response Technology (IRT).

4.1.5 Drug assignment and administration of doses for each patient

The treatment medication assignment for xentuzumab and placebo will be managed through an IRT system.

Everolimus and exemestane will be supplied to all investigator sites by the Sponsor, either via a local supplier not managed through the IRT system, or via the central depot along with the xentuzumab/placebo and managed through the IRT system.

4.1.5.1 Drug assignment and administration

Treatment will commence within 7 days of randomisation. Any exceptions to this must be discussed and agreed with the Sponsor.

Xentuzumab/Placebo

Patients will be treated with 1000 mg xentuzumab/placebo starting at C1V1. Xentuzumab/placebo will be administered at the investigator site intravenously over one hour with a constant infusion rate on the treatment day as specified in the [Flow Chart](#). If the scheduled infusion of xentuzumab/placebo is not performed within the time window, this treatment will be skipped. Subsequent visits will follow the original visit date schedule. Mannitol is used in the formulation of xentuzumab/placebo, so infusion duration of less than one hour must be avoided. The infusion time may be extended to over one hour and up to a maximum of three hours in cases of CTCAE grade ≥ 2 infusion reactions. In case of a delay or an interruption of infusion, the reason and the exact time of deviation must be recorded in the CRF. The accuracy of this information is crucial for the proper evaluation of PK and other data.

Detailed information of dispensation, preparation, and handling of xentuzumab/placebo will be described in the pharmacy manual/ISF.

Drug holidays for up to 14 calendar days (i.e. one missed xentuzumab infusion) e.g. vacation, are allowed, if previously agreed with the investigator. This is not considered non-compliance (for further details also refer to [Section 4.3](#)). Missed infusions due to recovery from AEs are not considered “Drug holidays”. Duration of drug holidays beyond

14 calendar days has to be agreed with the sponsor.

Everolimus

The recommended treatment dose for everolimus is 10 mg once daily. Complete guidelines for management and administration of everolimus can be found in the EU SmPC or the PI of the respective country. Please always refer to the current SmPC/PI for instructions. Treatment interruptions and dose adjustments should follow the SmPC/PI.

Everolimus will be prescribed by the investigator. Everolimus is supplied by the Sponsor and will be dispensed at visits described in the [Flow Chart](#) either by the investigator, site staff or the affiliated pharmacy through IRT. During the trial, patients may be administered a combination of different dose strengths of everolimus. For example, 10 mg everolimus can be given as one tablet of 10mg, two tablets of 5 mg or one tablet of 5 mg plus two tablets of 2.5 mg.

Per CTP version 6, the revised and reduced [flow chart](#) should be referenced.

Exemestane

The recommended treatment dose for exemestane is one 25 mg tablet once daily after a meal. Complete guidelines for management and administration of exemestane can be found in the EU SmPC or the PI of the respective country. Please always refer to the current SmPC/PI for instructions. Treatment interruptions should follow the SmPC/PI.

Exemestane will be prescribed by the investigator. Exemestane is supplied by the Sponsor and will be dispensed at visits described in the [Flow Chart](#) either by the investigator, site staff or the affiliated pharmacy through IRT.

Per CTP version 6, the revised and reduced [flow chart](#) should be referenced.

4.1.5.2 Temporary treatment pauses and dose reduction

Treatment pauses for each of the combination partners, i.e. xentuzumab/placebo, everolimus and exemestane are possible when AEs occur. For everolimus and exemestane, please refer to the current SmPC/PI. Dose reductions for treatment-related AEs are only recommended for everolimus. For details refer to the current SmPC/PI.

Xentuzumab/Placebo: For xentuzumab/placebo no dose reductions are allowed. In the event of an AE \geq CTCAE grade 3 considered to be related to xentuzumab, treatment should be paused until the patient has recovered from the drug-related toxicity to grade \leq 1 or baseline. Baseline is defined as the CTCAE grade at the start of treatment.

If a patient has not recovered to CTCAE grade \leq 1 or baseline within 14 days, continuation of treatment should be discussed with the sponsor. If the patient is deriving obvious clinical benefit according to the investigator's judgement, continuation of treatment with xentuzumab/placebo will be decided by the Sponsor and the investigator.

During temporary treatment pauses of xentuzumab/placebo, the scheduled drug infusion will be missed. Upon restart of xentuzumab/placebo treatment, infusions should be resumed according to regular visit schedule.

If grade 2 AEs persist for ≥ 7 days despite treatment and are poorly tolerated by the patient, the investigator may choose to pause but must resume treatment within 14 days. For recovery and continuation of treatment refer to previous paragraphs.

Xentuzumab/placebo, everolimus/exemestane: In case all treatment drugs need to be paused for recovery from treatment-related AEs, patients must resume treatment within 14 days. If the patient is not able to restart treatment within 14 days but is deriving obvious clinical benefit according to the investigator's judgement, continuation of treatment will be decided following agreement between the Sponsor and the investigator.

In the case of adverse events not considered related to xentuzumab, everolimus or exemestane, the study drug(s) may be interrupted for up to 14 days, but no dose reduction should occur. If the patient is not able to restart treatment within 14 days but is deriving obvious clinical benefit according to the investigator's judgement, continuation of treatment will be decided following agreement between the Sponsor and the investigator

4.1.6 Blinding and procedures for unblinding

4.1.6.1 Blinding

The trial will be performed according to a parallel-group, double-blind, placebo-controlled design. How long patients, investigators and everyone involved in trial conduct or analysis or with any other interest in this double-blind trial will remain blinded with regard to the randomised treatment assignments will be dependent upon whether or not the criterion for the seamless option is met. If the criterion for the seamless option is met then the trial will be expanded into a confirmatory Phase III trial and will remain double-blinded until the database lock for the primary PFS analysis time-point of the expanded trial. If the criterion is not met then the trial will be fully unblinded at the time of the database lock for the primary PFS time-point of the unexpanded Phase II trial. The randomisation code will be kept secret by Clinical Trial Support up to database lock for whichever primary analysis time point is applicable.

As no added benefit of xentuzumab compared to placebo was observed at the Phase II primary PFS analysis time-point, blinding of the trial in anyway is no longer necessary.

The independent DMC will have access to the unblinded treatment codes in order to allow them to periodically assess the trial data to ensure the overall safety and integrity of the trial, as well as to conduct the pre-specified Phase II primary PFS analysis detailed in [Section 7.4](#). For further details refer to [Section 8.7](#) as well as the DMC charter.

Due to a visible difference in xentuzumab versus placebo the pharmacy/dispensing team will be unblinded to treatment arm and an unblinded CRA will be employed to monitor compliance within the pharmacy department. Procedures to ensure blinding of the investigator and the trial team are documented in a separate blinding plan and filed in the TMF.

4.1.6.2 Unblinding and breaking the code

Emergency unblinding will be available to the investigator via IRT. It must only be used in an emergency situation when the identity of the trial drug must be known to the

investigator in order to provide appropriate medical treatment or otherwise assure safety of trial participants. The reason for unblinding must be documented in the source documents and/or appropriate CRF page along with the date and the initials of the person who broke the code.

Due to the requirements to report Suspected Unexpected Serious Adverse Reactions (SUSARs), it may be necessary for a representative from BI's Pharmacovigilance group to access the randomisation code for individual patients during trial conduct. The access to the code will only be given to authorised Pharmacovigilance representatives and not be shared further.

4.1.7 Packaging, labelling, and re-supply

The investigational product and the AMPs, if applicable, will be provided by BI or a designated CRO. They will be packaged and labelled in accordance with the principles of Good Manufacturing Practice (GMP). Re-supply to the sites will be managed via an IRT system, which will also monitor expiry dates of supplies available at the sites.

For details of packaging and the description of the label, refer to the ISF.

4.1.8 Storage conditions

Drug supplies will be kept in their original packaging and in a secure limited access storage area according to the recommended storage conditions on the medication label. A temperature log must be maintained for documentation. If the storage conditions are found to be outside the specified range, the unblinded CRA or appropriate back-up (as provided in the list of contacts) must be contacted immediately.

4.1.9 Drug accountability

The investigator and/or pharmacist and/or investigational drug storage manager will receive the investigational drugs delivered by the sponsor when the following requirements are fulfilled:

- Approval of the clinical trial protocol by the institutional review board (IRB) / ethics committee,
- Availability of a signed and dated clinical trial contract between the Sponsor and the investigational site,
- Approval/notification of the regulatory authority, e.g. competent authority,
- Availability of the curriculum vitae of the Principal Investigator,
- Availability of a signed and dated clinical trial protocol,
- Availability of the proof of a medical license for the Principal Investigator,
- Availability of FDA Form 1572 (if applicable).

Investigational drugs are not allowed to be used outside the context of this protocol. They must not be forwarded to other investigators or clinics.

The background treatment will be supplied by the Sponsor.

The investigator and/or pharmacist and/or investigational drug storage manager must maintain records of the IMP/AMP's delivery to the trial site, the inventory at the site, the

use by each patient, and the return to the sponsor or warehouse/drug distribution centre or alternative disposal of unused products at site. If applicable, the Sponsor or warehouse/drug distribution centre will maintain records of the disposal.

These records will include dates, quantities, batch/serial numbers, expiry ('use by') dates, and the unique code numbers assigned to the IMP/AMP and trial patients. The investigator/pharmacist/investigational drug storage manager will maintain records that document adequately that the patients were provided the doses specified by the clinical trial protocol (CTP) and reconcile all IMPs/AMPs received from the sponsor and/or provided by the investigational site. At the time of return to the sponsor and/or appointed contract research organisation (CRO)/destruction at site, the investigator/pharmacist/investigational drug storage manager must verify that all unused or partially used drug supplies have been returned by the clinical trial patient and that no remaining supplies are in the investigator's possession.

4.2 OTHER TREATMENTS, EMERGENCY PROCEDURES, RESTRICTIONS

4.2.1 Other treatments and emergency procedures

4.2.1.1 Rescue medication

Rescue medications to reverse the effects of xentuzumab/placebo are not available. Side effects of these treatments should be treated symptomatically. There is no specific antidote to overdosage of xentuzumab/placebo. For details regarding everolimus and exemestane refer to the current SmPC/PI.

4.2.1.2 Emergency procedures

There are no special emergency procedures to be followed that are specific for this protocol.

Precaution should be taken to avoid extravasation of xentuzumab/placebo. Patients should be asked to report any pain or burning at the site of injection immediately. If extravasation is suspected the infusion should be stopped immediately.

To date the only expected serious adverse reactions identified for xentuzumab are infusion-related reactions observed in patients who received xentuzumab treatment ([c01690707](#)).

Xentuzumab/placebo infusion should always be administered under close supervision of a medically qualified staff member with immediate availability of appropriate resuscitation facilities.

Infusion reactions may occur during xentuzumab/placebo infusions and include pyrexia, chills, rigors, dyspnoea, urticaria, bronchospasm, hypotension and hypertension. A one hour observation period is recommended following each infusion. If there is no infusion reaction during the first treatment cycle, the observation period following xentuzumab/placebo infusions may be adjusted at the discretion of the investigator. Mild to moderate infusion reactions may be managed with a slower infusion rate and prophylactic antihistamines for subsequent dosing. Severe reactions require immediate and

permanent discontinuation of infusion (see [Table 4.2.1.2: 1](#)).

The infusion reactions should be treated symptomatically as judged clinically relevant by the investigator. For symptomatic treatment of infusion reactions: hydrocortisone, antihistamines such as chlorphenamine accompanied by an antipyretic/analgesic and/or a bronchodilator is recommended. The infusion duration may be extended to over one hour and up to a maximum of three hours, see [Section 4.1.4](#).

Table 4.2.1.2: 1 Infusion reaction management

Infusion reaction grade	Description of event	Management
CTCAE grade 1 or 2	Grade 1: Mild transient reaction; infusion interruption not indicated; intervention not indicated Grade 2: Therapy or infusion interruption indicated but responds promptly to symptomatic treatment (e.g., antihistamines, NSAIDS, narcotics, i.v. fluids); prophylactic medications indicated for ≤24 h	In the event of CTCAE grade 1 infusion reactions, the infusion rate should be reduced by 50%. Grade 2 infusion reactions may require symptomatic treatment, as described to the left (with infusion interruption). Once the event has resolved, the infusion may be restarted at the reduced rate.
CTCAE grade 3	Grade 3: Prolonged (e.g., not rapidly responsive to symptomatic medication and/or brief interruption of infusion); recurrence of symptoms following initial improvement; hospitalization indicated for clinical sequelae	For patients experiencing CTCAE grade 3 infusion reactions, infusion should be interrupted immediately and patients should receive aggressive symptomatic treatment, as described above. Only after all the symptoms have disappeared, the infusion may be re-started if it is within 3 h since the infusion start. The infusion rate should be reduced by 50% after re-start.
CTCAE grade 4	Grade 4: Life-threatening consequences; urgent intervention indicated	Patients experiencing CTCAE grade 4 infusion reactions, such as anaphylaxis during an infusion, should have the infusion immediately stopped and receive appropriate treatment, as described above, including use of resuscitation if needed. Such patients should NOT receive any further xentuzumab/placebo treatment.

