The AEs observed during xentuzumab treatment to date have generally been of mild to moderate intensity (National Cancer Institute [NCI] Common Terminology Criteria for Adverse Events [CTCAE] grades 1 or 2) or consistent with the safety profile of combination backbone treatment or the underlying neoplastic conditions of patients enrolled into the studies. The most frequently reported AEs for xentuzumab monotherapy were fatigue, decreased appetite, nausea, diarrhoea, and vomiting. Abnormal liver enzyme elevation tests were observed at low frequencies and were generally of low grade (CTCAE grades 1 and 2) in all monotherapy studies. No cases of drug-induced liver injury were reported. There were no signs of cardiac toxicity, and no laboratory findings that would indicate kidney damage in patients treated with xentuzumab. No clinically relevant hyperglycaemia has been observed so far.

The most frequently reported serious adverse events (SAE) for xentuzumab monotherapy were dyspnoea and pneumonia. AEs leading to death were reported for 3 patients (acute respiratory failure, dyspnoea, and malignant neoplasm progression); none of these events was considered by the investigator to be related to xentuzumab.

To date the only expected serious adverse reactions identified for xentuzumab are

infusion- related reactions observed in patients who received xentuzumab treatment ([c01690707](#)).

Anti-tumour activity has been observed in the Phase I monotherapy study 1280.1, with 2 partial responses according to Response Evaluation Criteria In Solid Tumors (RECIST, [R09-0262](#)) criteria in a patient with nasopharyngeal cancer and a patient with a peripheral primitive neuroectodermal tumor/Ewing sarcoma and 2 patients with partial response in the Phase I monotherapy study 1280.15. In addition, considerable proportions (12% to 45%) of heavily pre-treated patients in the Phase I monotherapy studies were reported with stable disease when treated with xentuzumab.

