- Fluconazol oral 100 mg daily in case of no improvement with topical antifungal treatment with nystatin. Please note that fluconazole is a moderate inhibitor of CYP 3A4, which may potentially have an impact on metabolism of everolimus and exemestane.
- Systemic antiherpetic therapy (i.e. Famvir 750 mg/d for 7 days otherwise Aciclovir oral or i.v.) at investigator's discretion.

For dose reduction, interruption or discontinuation of everolimus in the management of stomatitis, refer to the current EU SmPC of everolimus or the PI of the respective country.

Table 4.4.1.2: 1 Grade-specific treatment recommendations of mucositis/stomatitis

Severity (CTCAE grading)	Description	Treatment recommendations*
Mild (Grade 1)	Asymptomatic or mild symptoms; intervention not indicated	
For sites with access to dexamethasone containing mouthwashes: Swish 10 mL of a 0.9% saltwater solution and spit, followed by the same regimen of dexamethasone mouthwash as in section 4.4.1.1 10–15 min later.
 
For sites without access to dexamethasone containing mouthwashes: Refer to 4.4.1.1

Severity (CTCAE grading)	Description	Treatment recommendations*
Moderate (Grade 2)	Moderate pain or ulcer that does not interfere with oral intake; modified diet indicated	Addition of topical analgesic mouth treatments, topical corticosteroids, antiviral therapy if herpetic infection confirmed, antifungal therapy preferably topical on a case by case basis.
Severe (Grade 3)	Severe pain; interfering with oral intake	Same as for grade 2; institute additional symptomatic therapy (topical or systemic) as clinically indicated.
Life threatening (Grade 4)	Life-threatening consequences; urgent intervention indicated	Same as for grade 2; institute additional symptomatic therapy (topical or systemic) as clinically indicated.

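### Protocol Section 4.2.1.2 gives conflicting instructions for CTCAE grade 3 infusion reactions: the text calls for a permanent stop, while the table it cites permits the same infusion to be re-started

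*Protocol*

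**What the plan says.** Protocol Section 4.2.1.2 gives its instructions twice, once in text and once in Table 4.2.1.2: 1.

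The text has two severity tiers:
- Lower tier: "Mild to moderate infusion reactions may be managed with a slower infusion rate and prophylactic antihistamines for subsequent dosing".
- Upper tier, in a sentence that a page break splits in two: "Severe reactions require immediate and" and then "permanent discontinuation of infusion". This sentence ends by citing the table.

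The table works by CTCAE grade:
- Grades 1 and 2 share a row that provides for a reduced rate, with interruption and symptomatic treatment where needed at grade 2.
- Grade 3 calls for immediate interruption and symptomatic treatment, and continues: "Only after all the symptoms have disappeared, the infusion may be re-started if it is within 3 h since the infusion start". It adds: "The infusion rate should be reduced by 50% after re-start".
- Grade 4 calls for an immediate stop and ends: "Such patients should NOT receive any further xentuzumab/placebo treatment".

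**The concern.** The upper-tier sentence and the grade 3 row appear to cover the same patient and to give opposite instructions. One ends the infusion for good. The other lets the same infusion resume once symptoms have gone. Because the text cites the table as its own detail, the two cannot be set aside as rules for different situations.

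The subject matters because the same section names infusion-related reactions as the only expected serious adverse reactions identified for xentuzumab. A site that re-starts after a grade 3 reaction follows the table and departs from the text. A site that stops for good follows the text and forgoes something the table allows.

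The same question arises later, when protocol deviations are reviewed. SAP Table 6.2: 1 has code C2 for trial medication not given as the protocol directs and code C3 for infusion times outside protocol limits. Where the protocol gives two answers, a reviewer judging a re-started grade 3 infusion needs to know which passage governs.

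**Working it through.** No arithmetic applies. The check sets the passages side by side, tests the two undefined terms, and looks for a reconciling rule.

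**Step 1: compare by grade, reading 'severe' as grade 3 and above.**

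| CTCAE grade | Text of Section 4.2.1.2 | Table 4.2.1.2: 1 | Compatible? |
|---|---|---|---|
| 1 and 2 | May be managed with a slower rate and antihistamines at later doses | Reduced rate; grade 2 may need interruption, then re-start | Yes |
| 3 | Stop at once and permanently | Interrupt; re-start permitted within 3 h of infusion start, at half rate | No |
| 4 | Stop at once and permanently | Stop; no further xentuzumab/placebo | Yes |

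The conflict is confined to grade 3.

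**Step 2: does 'severe' include grade 3?** Section 4.2.1.2 does not say. In the table itself the grade 3 description does not use the word. Usage elsewhere in the protocol:
- Section 1.2.1 describes adverse events under xentuzumab as having "generally been of mild to moderate intensity (National Cancer Institute [NCI] Common Terminology Criteria for Adverse Events [CTCAE] grades 1 or 2". The lower tier of the text uses the same words, so it corresponds to grades 1 and 2.
- Table 4.4.1.2: 1 (stomatitis) labels its third row "Severe (Grade 3" and gives grade 4 a separate label, life threatening.
- Table 10.2.1: 1 (diarrhoea) labels the two grades in the same way.
- Section 4.4.4 writes severe neutropenia and defines it in brackets as grade 3 or higher.

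All four point the same way: grade 3 is not mild to moderate, and it is severe. If 'severe' meant grade 4 alone, the two tiers of the text would leave grade 3 without a rule there.

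**Step 3: what does 'discontinuation of infusion' cover?** Two meanings are possible.
- That infusion only. The table re-starts that same infusion, so the conflict remains.
- All further xentuzumab/placebo. The table reserves that for grade 4, so the conflict remains and is wider.

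The conflict therefore depends on the meaning of 'severe', not on the meaning of 'discontinuation'. The second term still needs defining, because the two meanings have different consequences for later doses.

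**Step 4: does another section settle it?**
- Section 4.1.5.1 allows a longer infusion for reactions of grade 2 and above but does not say when an infusion must end for good.
- Section 4.1.5.2 has a general pause rule for xentuzumab-related events of grade 3 and above but does not mention infusion reactions.
- Section 4.4 sends the reader back to Table 4.2.1.2: 1.

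None of these decides between the text and the table.

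**The case against.** The best defence is that 'severe' is undefined here and that the text hands over to the table. On that view the table is the operative detail, its only permanent stop is grade 4, and 'severe' in the text is shorthand for grade 4. The labels in the stomatitis and diarrhoea tables were written for other events. This reading would remove the conflict. It is possible, but it goes against every other use of the word cited above, including the explicit bracket in Section 4.4.4, and against the two-tier wording of the text. What stands is that the conflict rests on usage rather than on a definition in Section 4.2.1.2.

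A second defence is that these are not strict instructions. Section 4.2.1.2 opens by saying that the protocol has no special emergency procedures of its own, and Section 4.4 says infusion reactions are treated by standard of care or local guidance, with the table as additional guidance. This softens the practical effect. It does not remove the inconsistency, since the sentence on severe reactions uses the word 'require'.

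A third defence is that the matter is largely past. Sections 1.4 and 4.1 record the recommendation of 29 September 2021 to stop xentuzumab and placebo, and the reduced flow chart dispenses only everolimus and exemestane. Section 1.4 also describes these reactions as mostly grade 1 and 2. This stands and limits the size of the point.

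A reader might also infer two further conflicts, which the documents do not support:
- **The table's 3 h limit against the three-hour maximum infusion time** in Sections 4.1.5.1 and 4.2.1.2 and Table 4.1.1: 1. A re-start can satisfy both limits, and infusion procedure is delegated to a pharmacy manual that is not part of these documents.
- **The table against the pause rule in Section 4.1.5.2.** The table's condition that all symptoms have gone is at least as strict as recovery to grade 1 or baseline, so the recovery conditions do not clash.

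**Conclusion.** The concern holds as a minor inconsistency in a safety instruction. For grade 3 infusion reactions the text and the table of Section 4.2.1.2 cannot both be followed. This assumes that 'severe' carries the meaning it has elsewhere in the protocol. It does not depend on how 'discontinuation of infusion' is read.

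Its size cannot be put as a number: the documents give no count of grade 3 infusion reactions, and no figure in the protocol or SAP depends on the point. A reader might infer that the inconsistency could alter the analysis populations or the efficacy result. The SAP does not support that. Section 6.2 plans no per-protocol analysis, and codes C2 and C3 are listed as excluding patients from no analysis set. That list is also described as a working list that may not be final until the meetings before database lock, so there is a forum for settling how such infusions are judged.

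Nor is there a reporting gap. SAP Section 7.8.1 already plans an overall adverse event summary with categories for action taken and infusion related reaction response, and a summary of infusion related reactions by highest CTCAE grade.

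**What to change.** The sponsor should reconcile the text of Section 4.2.1.2 with Table 4.2.1.2: 1 so that each CTCAE grade has one stated action, and should say whether 'discontinuation of infusion' means the infusion in progress or all further xentuzumab/placebo. Which clinical rule applies is for the sponsor to decide.

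If no further amendment is planned, the clinical trial report should state in one sentence which of the two passages was used to judge infusions already given.

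As a clerical correction, the same section cites Section 4.1.4 for extending the infusion, but that section covers assignment to treatment groups.

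The cost is a short change of wording, or one sentence in the report. No new data or extra outputs are needed: Section 4.1.5.1 already requires the reason for and exact time of any interruption to be recorded in the CRF.
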